5.1 Primary objectives

To investigate the efficacy of a single pre-operative 1g dose of oral flucloxacillin in preventing SSI within 30 days in adults undergoing surgical excision of an ulcerated skin cancer under local anaesthetic with planned wound closure.

• PICO summary

Population: Adults undergoing surgical excision of an ulcerated skin cancer under local anaesthetic with planned wound closure

Intervention: pre- operative oral flucloxacillin 1g (500mg x 2) in addition to standard clinical care

Comparator: no antibiotic (placebo) and standard clinical care

Outcome: SSI within 30 days using CDC criteria (16)

5.2 Secondary objectives

- To assess the adverse events of a single dose (1g) of oral flucloxacillin.
- To investigate antibiotic resistance in infected wounds.
- To evaluate the cost effectiveness of oral flucloxacillin and no antibiotic treatment.
- To evaluate participants' and clinicians' views on oral antibiotics in preventing wound infection.
- To investigate the feasibility of 'Selfi-wound' photos.
- To validate the WHQ for SSI assessment in skin surgery.

5.3 Tertiary objectives

To explore patient wound burden

5.4 Primary outcomes measure

To compare the proportion of participants in the oral flucloxacillin group with the no antibiotic (placebo) group diagnosed with Surgical Site Infection within 30 days post-randomisation.

5.5 Secondary outcomes measures

• The number of participants with adverse events within 30 days of surgery using the Medical Dictionary for Regulatory Activities.

- Antibiotic resistance to clinically relevant antibiotics will be evaluated in isolates from participants' wounds at diagnosis of SSI and after 7 days if no response to treatment. This will be assessed by a central microbiology laboratory (Public Health Wales).
- Health-related QoL measured by EQ-5D-5L questionnaires at baseline, 30 days and 3 months.
- Time to return to normal activity/work at 30 days and 3 months.
- Resource use (related to wound complications including SSI) and cost of hospital visits/stays at 30 days and 3 months.
- Qualitative process evaluation assessing implementation and acceptability of oral antibiotics including facilitators and barriers.
- Feasibility of 'Selfi-wound' photos as measured by the number of participants who were able to successfully take and transmit an image of their wound images via the online system.
- Validation of WHQ remote use for SSI assessment via SWAT.

5.6 Tertiary outcome

• Qualitative process evaluation process exploring participant wound burden.

6 Trial design and setting

EXCISE is a randomised, participant, clinician and assessor-blinded, placebo-controlled trial (with internal pilot) comparing oral flucloxacillin versus no antibiotic (placebo) in adult patients undergoing ulcerated skin cancer excision in NHS UK hospitals under local anaesthetic with planned wound closure.

The trial will be undertaken in 10-15 sites across the UK. Co-applicants encompass 5 of these sites who will be Principal Investigators, members of the Trial Management Group (TMG), and lead recruiting sites (Cardiff, Oxford, Fife, Hull and Walsall). Further additional sites will be opened as required.

6.1 Risk assessment

A Trial Risk Assessment has been completed to identify the potential hazards associated with the trial and to assess the likelihood of those hazards occurring and resulting in harm. This risk assessment has been completed in accordance with the Medical Research Council/Department of Health/Medicine and Healthcare products Regulatory Agency (MRC/DH/MHRA) Joint project guidance document 'Risk-adapted approaches to the management of Clinical Trials of Investigational Medicinal Products' and includes:

The known and potential risks and benefits to human subjects

- How high the risk is compared to normal standard practice
- How the risk will be minimised/managed

This trial has been categorised as a TYPE A, where the level of risk is no higher than the risk of standard medical care. A copy of the trial risk assessment may be requested from the Trial Manager. The trial risk assessment is used to determine the intensity and focus of monitoring activity (see section 24.1).

This clinical trial is to be conducted in compliance with the protocol, the EU Clinical Trial Regulation 536/2014 and Good Clinical Practice (GCP).

7 Site and Investigator selection

This trial will be carried out at 10-15 participating sites within the UK. All sites who are interested in participating in the trial will be required to complete a registration form to confirm that they have adequate resources and experience to conduct the trial. Where electronic health records are being used, Site teams must be willing and able to take steps to avoid unintentional unblinding through EHR system.

Before any Site can begin recruitment a Principal Investigator at each site must be identified. The following documents must be in place and copies sent to [contact]:

- > Confirmation of Capacity and Capability (C&C) from R&D department following sharing of local information pack.
- Favourable opinion of host care organisation/PI from Main Ethics committee.
- MHRA approval.
- A signed Trial Agreement.
- > Current Curriculum Vitae and GCP training certificate of the Principal Investigator (PI).
- ➤ Completed Site Delegation Log and Roles and Responsibilities document.
- > Full contact details for all host care organisation personnel involved, indicating preferred contact.
- A copy of the most recent approved version of the Participant Information Sheet(s)(PIS) and Consent Form(s) (ICF) on host care organisation headed paper.
- A copy of the most recent approved GP letter on host care organisation headed paper.
- Returned copy of the Source Data Agreement signed by the PI.
- Pharmacy confirmation that they have received the first shipment of IMP prior to opening the site. N.B. This is not a regulatory requirement more good practice.

Upon receipt of all the above documents, the Trial Manager will send written confirmation to the Principal Investigator/lead Research Nurse detailing that the centre is now ready to recruit participants into the trial. This letter/email must be filed in each site's Site File. Along with the written confirmation, the site should receive their trial drug supplies and a trial pack holding all the documents required to recruit into the Trial.

Occasionally during the trial, amendments may be made to the trial documentation listed above. CTR will issue the site with the latest version of the documents as soon as they become available. It is the responsibility of

the CTR to ensure that they obtain local R&D approval for the new documents. Site initiation will be by an online meeting.

The Trial Management Group (TMG) will apply for the trial to be registered with the Associate PI (API) scheme run by NIHR and will encourage the PI at each site to recruit a healthcare professional early in their research career to consider registering with the scheme.

8 Participant selection

Participants are eligible for the trial if they meet all of the following inclusion criteria and none of the exclusion criteria apply. All queries about participant eligibility should be directed to the Trial Manager before randomisation/registration. Sites are encouraged to recruit a broad range of participants, including with respect to ethnic diversity, socio-economic status, digital/health literacy and age.

8.1 Inclusion criteria

- Adult patients (≥ 16) with a clinically ulcerated suspected skin cancer (at any body site) listed for excision under local anaesthetic with planned wound closure by any secondary care speciality.
- 2) First time in the EXCISE trial.
- 3) Ability to provide informed consent (by participant or through a participant's personal legal representative).

8.2 Exclusion criteria

- 1) Clinical evidence of skin cancer infection at baseline using CDC criteria.
- 2) Skin tumour removal planned with curettage, Mohs micrographic surgery/ margin-controlled excision or shave excision.
- 3) Wound left for delayed reconstruction or secondary intention healing or closed with dermal substitute.
- 4) Concurrent oral antibiotic treatment (<24 hours after last dose).
- 5) Documented poor renal function (creatinine clearance < 10ml/min).
- 6) Previous allergic reaction to penicillin.

9 Recruitment, Screening and registration

9.1 Internal Pilot

We have included a planned internal pilot phase, using quantitative and qualitative data, during the first 6 months of recruitment (study months 10-15). We will review recruitment sites and participant enrolment, completeness of primary outcome data, including surgical technique adherence and a clinical review of a subset of patients who do not report a suspected SSI (see Table 1 below for Pilot Progression Criteria). We will also conduct a rapid qualitative evaluation from interviews with a sub-sample of participants and HCPs to

examine the acceptability of recruitment and trial processes, attitudes about antibiotics, as well as an early assessment of clinical equipoise and contextual factors that may affect implementation (36,37).

Our recruitment estimates for the pilot phase have considered published reviews and recommendations (38-40), and that recruitment rates are slower when sites initially open. We plan for all sites to be open within the first 6 months with a staggered opening rate and slower recruitment rates in the first few months.

Pooled data of NIHR funded studies show that internal pilots typically recruit 15% of their participants within 33% of the total recruiting time period (38). These figures have been used to calculate the number of participants expected to be recruited, (n=57; 15% of 380) in 6 months (33% of the total 15-month recruitment window). This 6-month window will start when the first site is open to recruitment. We will use a traffic light system to determine feasibility and have developed a recruitment prediction based on our feasibility data, recent expressions of interest and experience on speed of site opening.

We will also monitor the proportion of participants providing primary outcome data. We would anticipate a completion rate of 85%, rates below this (<84%) will prompt a review of the process of capturing primary outcome data. We will actively monitor the SSI rate during the pilot phase of the trial, reporting these to our Independent Data Monitoring Committee (IDMC). Participants will be asked to complete a daily diary, which will record any concerns about wound infection and side effects. We also plan to record surgeon compliance with WHO surgery technique recommendations.

Table 1. Internal Pilot Progression Criteria

Progression criteria at 6 months	Red	Amber	Green
Recruitment rate/site/month	≤60% (n ≤1.2)	61-99% (1.3 ≥ n ≤1.9)	100% (n ≥2.0)
Number of sites opened	≤25% (n ≤2)	26%-99% (3 ≥ n ≤7)	100% (n≥ 8)
Total number of participants recruited	≤60% (n ≤34)	61-99% (35 ≥ n ≤56)	100% (n≥57)

We will use the Guidance for Reporting Involvement of Patients and the Public (GRIPP2) tool (41) for assessing the impact of patient and public involvement (PPI) and the feedback from qualitative interviews to understand the quantitative data and provide areas for improvement in processes to enhance the efficiency of the trial. The progression criteria have been designed to allow for mitigating strategies to be discussed to allow for some adaptation to recruitment processes.

We will constantly be assessing the criteria during the internal pilot phase. We will discuss the results with our Trial Steering Committee, before reporting to the NIHR HTA Programme.

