9.1.1 Recruitment rates

In our observational feasibility study, the average recruitment was 4.11 patients per month, from 3 open sites (Cardiff, Oxford and Birmingham) over a 12-month period (24). During the internal pilot phase, we predict the average recruitment rate would be 2.07 participants/site/month, which accounts for slower recruitment as sites open. The remaining recruitment time after the internal pilot is completed (9 months) would need to average 4.15 participants/site/month. PI co-applicants and expression of interest from other sites come from similar sized hospitals as those that took part in our feasibility study, therefore the recruitment rates proposed here should be achievable. We will review eligibility rates and reasons for exclusions to ensure we are being as inclusive as possible.

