At a local level, we will interact with and promote research findings through wider NHS Trusts and the NIHR Clinical Research Networks. Nationally we will engage with NICE and professional surgical organisations/societies, as well as national charities (such as CRUK, Melanoma Focus, Melanoma UK, SKCIN,

UK DCTN). We anticipate the results will directly impact clinical guidelines, which to date do not include recommendations regarding antibiotic use to prevent SSI in skin surgery.

27 Milestones

The EXCISE trial is a 36-month trial with the following project timeline:

- Month 1-9: Trial set-up, contracts, regulatory approvals, Investigational Medicinal Product manufacture.
- Month 10-15: Internal pilot, site set-up and recruitment.
- Month 16: Review of internal pilot.
- Month 16-24: Complete recruitment.
- Month 30: Last participant last follow-up.
- Month 31-36: Data cleaning, analysis, prepare papers and report; stakeholder event.

28 References

- 2. Cancer Research UK. Statistics by cancer type. Available at: Statistics by cancer type | Cancer Research UK [last accessed 05/12/23].
- 3. Levell N. Dermatology GIRFT Programme National Specialty Report 2021. Available at: Dermatology Getting It Right First Time GIRFT [last accessed 04/12/23].

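### The pilot target of 57 treats 6 of 15 months as 33% when it is 40%, and the site count and recruitment rates beside it do not fit the planned 10-15 sites

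*Protocol*

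**What the plan says.** Section 9.1 of the protocol cites pooled experience that "internal pilots typically recruit 15% of their participants within 33% of the total recruiting time period" and applies it to this trial: "n=57; 15% of 380) in 6 months (33% of the total 15-month recruitment window". The pilot runs "during the first 6 months of recruitment (study months 10-15". On sites, the same section states: "We plan for all sites to be open within the first 6 months".

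Table 1 sets green at 2.0 or more participants per site per month, 8 or more sites opened (labelled 100%) and 57 or more participants recruited. The Synopsis and sections 6 and 7 plan 10-15 sites.

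Section 9.1.1 predicts 2.07 participants per site per month during the pilot, and then: "The remaining recruitment time after the internal pilot is completed (9 months) would need to average 4.15 participants/site/month". It supports these rates with the feasibility study, in which "the average recruitment was 4.11 patients per month, from 3 open sites" over 12 months. Section 4 puts that study's recruitment at 148 participants. Section 27 gives months 10-15 for the pilot and months 16-24 for completing recruitment.

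**The concern.** Six months is not 33% of 15 months, and the protocol says these percentages were used to calculate 57. The error therefore feeds a threshold in the progression table and is more than a wording slip. The site and rate figures around it also appear to rest on a smaller trial than the one described elsewhere.

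Table 1 is what the Trial Steering Committee discusses and the funder receives, and section 15.6 allows the trial to end early on the funder's assessment against these targets. If the rows rest on different assumptions about window length and number of sites, a green result is hard to interpret. The treatment comparison itself is not affected.

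**Working it through.** **Inputs.** Total 380, benchmark 15% in 33%, pilot 6 months, window 15 months (section 9.1). Remaining time 9 months, rates 2.07 and 4.15 per site per month, feasibility rate 4.11 (section 9.1.1). Green thresholds 2.0, 8 and 57 (Table 1). Sites 10-15 (Synopsis, sections 6 and 7). Feasibility total 148 (section 4).

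**1. Reproducing 57.** 0.15 × 380 = 57. This agrees. The red limit also follows: 0.60 × 57 = 34.2, shown as 34.

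**2. Share of time.** 6/15 = 0.40, not 0.33. The 15 months is not an isolated figure: section 9.1.1 leaves 9 months after the pilot (6 + 9 = 15), and section 27 gives months 10-15 and 16-24 (6 + 9 = 15).

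**3. Where the benchmark puts 57.** 0.33 × 15 = 4.95, so about month 5.

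**4. Benchmark moved to month 6.** Proportional scaling from month 5 gives 57 × 6/5 = 68.4. With 0.33 unrounded to one third it is 380 × 0.15 × 0.40/0.33 = 69.1. Proportional accrual is an assumption; if accrual is still accelerating, as the staggered opening suggests, the figure is higher.

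**5. Base for the site row.** The red limit of 25% is 2 sites, and 0.25 × 8 = 2. Table 1 therefore treats 8 as the full complement.

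**6. Sites implied by 4.15.** Still to recruit: 380 − 57 = 323. Per month: 323/9 = 35.9. Sites: 323/(9 × 4.15) = 8.65. The rate needed for given numbers of sites is:

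| Sites | Needed per site per month (323/9/sites) |
|---|---|
| 8 | 4.49 |
| 10 | 3.59 |
| 15 | 2.39 |

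The stated 4.15 matches none of these.

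**7. Does 57 fit the site-opening forecast?** 57/2.07 = 27.5 site-months. Assume S sites open evenly over 6 months. Site-months are then 3 × S if each month's new sites count for half of it, or 3.5 × S if they count for all of it.
- 8 sites: 24 to 28 site-months, × 2.07 = 50 to 58 participants.
- 10 sites: 30 to 35 site-months, × 2.07 = 62 to 72 participants.

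So 57 fits about 8 sites, and the planned minimum of 10 would give more. Even opening is an assumption, since the protocol gives no opening schedule.

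**8. Feasibility rate.** As written, 4.11 per month from 3 sites is 4.11/3 = 1.37 per site per month. But 148/12/3 = 4.11, so the figure is already per site per month.

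**The case against.** The best defence is that 57 does not stand on the benchmark alone. Section 9.1 also mentions a forecast from feasibility data, expressions of interest and experience of site opening, and step 7 shows that 57 is close to what 8 evenly opening sites would give. That stands, and it is why the fix allows 57 to be kept on that basis. It does not rescue the 33%, and it ties the target to 8 sites.

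The 8 might be an interim count, since section 6 says further sites will be added as needed. But Table 1 labels 8 as 100%, and section 9.1 plans for every site to be open by the end of the pilot.

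Table 1 is also not a mechanical stop/go rule: it allows for mitigation, and the committees and funder exercise judgement. This limits the consequence of the errors.

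A reader might infer something stronger, that an all-green pilot is on course for only about half the sample: 57 + 9 × 2.0 × 8 = 201, or 53% of 380. The documents do not support this as a consequence of the 33% error. With a target of 69 the same projection gives 69 + 144 = 213 (56%), so the shortfall comes from holding 2.0 per site per month and 8 sites flat. The protocol does not plan a flat rate: section 9.1.1 states openly that the later rate "would need to average 4.15 participants/site/month". With 10 sites at the feasibility rate, 57 + 9 × 4.11 × 10 = 427, above 380. What remains is narrower: no row of Table 1 refers to the rise in rate on which the plan depends.

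A reader might also take "Month 30: Last participant last follow-up" (section 27) as a sign of an intended 18-month window, in which 6 months would be 33%. Recruitment ending in month 24 plus 3 months of follow-up reaches month 27; the rest is slack, not a contradiction. The 15 months is stated consistently, so an 18-month plan is conjecture.

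**Conclusion.** The concern holds for the figures as written. Six months is 40% of the stated window, and the benchmark reaches 57 about a month before the pilot ends. The month-6 green threshold is about 11 participants below its stated basis (68 against 57) under proportional scaling. That size depends on the assumed accrual shape; the direction does not, provided recruitment continues between months 5 and 6.

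Separately, 100% of sites is set at 8 against a planned 10-15, and 4.15 per site per month belongs to 8.65 sites. The feasibility rate lacks the words that make it per site, which is a minor correction but matters because the section relies on it to call the proposed rates achievable.

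None of this shows that 380 is out of reach. With 10 sites, 3.59 per site per month would be enough after a pilot that recruits 57, which is below the feasibility rate of 4.11. The point is worth correcting because these figures form the stated progression rule.

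**What to change.** Edit sections 9.1 and 9.1.1 and Table 1:

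- Change 33% to 40%.
- Either recompute the participant row for 40% of the window (green from about 68, red at or below 0.60 × 68.4 = 41, amber between), or drop the benchmark as its basis and justify 57 from the site-opening forecast, showing the forecast.
- Set 100% of sites to the planned minimum of 10, and recompute the participant row and the post-pilot rate on that same number. With 10 sites the later rate is 3.59 per site per month if 57 are recruited in the pilot, or (380 − 68)/9/10 = 3.47 if 68 are. Keeping 57 alongside 10 sites would need its own justification, given step 7 of the working.
- State the feasibility rate as 4.11 per site per month.
- Add beside Table 1 that green at 2.0 per site per month reaches 380 only if the rate then rises to the recomputed post-pilot figure.

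The cost is text changes and a traffic light that is slightly harder to pass. No extra participants are needed, and the recruitment window and sample size are unchanged.

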9.1.1 Recruitment rates

In our observational feasibility study, the average recruitment was 4.11 patients per month, from 3 open sites (Cardiff, Oxford and Birmingham) over a 12-month period (24). During the internal pilot phase, we predict the average recruitment rate would be 2.07 participants/site/month, which accounts for slower recruitment as sites open. The remaining recruitment time after the internal pilot is completed (9 months) would need to average 4.15 participants/site/month. PI co-applicants and expression of interest from other sites come from similar sized hospitals as those that took part in our feasibility study, therefore the recruitment rates proposed here should be achievable. We will review eligibility rates and reasons for exclusions to ensure we are being as inclusive as possible.

9.2 Participant identification

Potential participants will be identified through the NHS care pathway during their initial consultation for their skin cancer excision. Once a patient has been identified as potentially eligible to participate, the opportunity will be discussed with the patients, and they will be given a copy of the trial PIS and ICF. The patient will be given adequate time to consider the trial and given the opportunity to ask further questions.

Our feasibility study, OASIS (24) showed that the average age of patients in this study population was 77 years old. We have designed the trial in line with best practice recommendations for research involving older people (42) and developed our patient facing materials using the NIHR INCLUDE Impaired Capacity to Consent Framework to ensure accessibility of the trial for those with cognitive and other impairments (43).

Information will be provided in a range of materials and formats such as large print versions, summary information sheets, and an infographic recruitment video, developed in consultation with our PPI representatives to ensure the information is accessible, including those with cognitive and/or communication impairments such as poor vision.

Participants should be encouraged to discuss the trial with their friends and family if they wish who can support them to decide about participating and/or support them to take part.

The right of the participant to refuse to participate in the trial without giving reasons must be respected. However eligible participants who refuse to participate will be approached to ask for their reason following the SEAR framework for monitoring recruitment and inclusivity (44).

The PI or nominated delegate listed on the trial delegation log must confirm eligibility of a patient in the patient's medical notes and by completing the Eligibility checklist prior to enrolment. Randomisation will only be possible once the patient's eligibility is confirmed.

